#### 1. Project Overview

**1.1. Summary of relevant research findings leading to this research proposal** Obesity and high blood pressure are contributing factors to cardiovascular disease (CVD), a clinical condition which causes approximately 18 million deaths in the United States. The Southeastern United States contains four of the top five states with the highest adult obesity rates. Nutrition interventions promoting healthy food habits and choices can manage obesity and cardiovascular disease. However, recent studies have shown 12-week nutritional interventions promoting the dietary patterns of those seen in the Mediterranean, coupled with the supplementation of extra virgin olive oil (EVOO) or mixed nuts, are very effective in reducing the risk of CVD and cardiovascular events (1,2,3)

# **1.2.** Brief description of methodology, including design, population, and variables of interest

This will be a prospective randomized controlled trial of Auburn University (AU) employees or an adult sponsored dependent of an active employee (<18 years old) who was insured by the AU Health and Pharmacy Insurance plan during 2015 and enrolled in the Health Insurance plan for 2016 and/or 2017. Eligible patients are 1) those completing their "Healthy Tigers" biometric screening between 01/01/2015-5/31/16, 2) who had a BMI  $\geq$  30 and two or more of the following CVD risk factors: male, age 55-80; female, age 60-80; current smoker; family history of premature coronary heart disease; received a red or yellow zone reading for their blood pressure, blood glucose, total cholesterol; those with a diagnosis of hypertension, pre-diabetes, or hypercholsterolemia; a patient of the AU Employee Pharmacy enrolled in the TigerMeds program with an existing diagnosis of hypertension, pre-diabetes, or hypercholesterolemia. Patients will be randomized into two groups: the AHA vs MD. The study will consist of a 12-week nutrition education program that includes dietary nutrition education sessions (both groups) and extra virgin olive oil and mixed nut supplementation (MD group). We will assess program impact by comparing baseline characteristics including body mass index, blood pressure, blood glucose, and total cholesterol, etc., and reassessing the same measures at week 6 and week 12 of the study.

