#### 2. Purpose

#### 2.1. Purpose of this project including research questions and/or aims

The primary objective of this pilot study is to assess the efficacy of a MD intervention (education + EVOO and mixed nut supplementation) versus that of an AHA nutrition intervention (education) on serum blood lipid levels as markers for cardiovascular disease risk. As secondary outcomes we will assess insulin resistance, serum metabolic factors, blood pressure, body mass index, and waist circumference.

Research Question: In the Southeastern United States, is the dietary pattern of the American Heart Association or a Mediterranean style diet more effective in the reduction of CVD risk factors.

Aim 1: To assess whether or not patients have improvements in their CVD risk factors by the end of the 12-week program.

Aim 2: To assess which dietary intervention is most effective in the reduction of CVD risk factors at the end of the 12-week program.

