### 3. Participants

#### 3.1. Inclusion and exclusion criteria

a) Inclusion Criteria:

Auburn University employees or an adult sponsored dependent of an active employee who was insured by the Auburn University Health and Pharmacy Insurance Plan during 2015 and/or 2016 and who are enrolled in the Auburn University Health Plan for the 2017 plan year, who meet the following criteria:

- Have completed their "Healthy Tigers" screening for the 2015, 2016, or 2017 plan year (completed by the "Healthy Tigers" staff or through submission of a "Healthy Tigers" healthcare provider form OR is a patient of the AU Employee Pharmacy and is enrolled in the TigerMeds program OR is a participant in the Pharmacy Practice Experience (PPE) who is seen within the AUPCC AND has a BMI (kg/m2) screening value >24.9 AND has two or more of the following CVD risk factors:
  - a) screening values classified in the "yellow" or "red" zone for:
    - Systolic blood pressure (mmHg): Yellow zone:  $\ge$ 140, Red zone:  $\ge$ 160;
    - Diastolic Blood pressure (mmHg): Yellow zone: ≥90, Red zone: ≥ 100;
    - Fasting blood glucose (mm/dL): Yellow zone:  $\geq$ 100, Red zone:  $\geq$ 126
    - Blood glucose(random) (mg/dL): Yellow zone: 140-200, Red zone > 200
    - Total Cholesterol (mg/dL): Yellow zone:  $\geq$ 200, red zone:  $\geq$ 250
  - b) Have a pre-existing diagnosis of hypertension, pre-diabetes, or hypercholesterolemia
  - c) Current smoker ( $\geq 1$  cigarette/day)
  - d) Are: male (age: 55-80) or female (age: 60-80)
  - e) A family history of premature coronary heart disease
  - f) High risk ethnicity: Black, African American, American Indians/Alaska Natives, Non-Hispanic blacks, Mexican-Americans, Asian, Hispanic/Latino

- b) Exclusion Criteria:
  - 1. Minors that are less than 19 years of age
  - 2. Individuals who are not enrolled in the Auburn University health insurance program for the 2016 plan year at baseline and have not yet completed initial visit
  - Individuals who have not completed their 2015 "Healthy Tigers" biometric screening between January 1st and December 31st, 2015 (these can be completed by the "Healthy Tigers" staff or by submitting a healthcare provider form from the individuals' physician to the "Healthy Tigers" office), unless enrolled in TigerMeds.
  - 4. Individuals who are pregnant or who intend to become pregnant during the 12-week health and wellness challenge.

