  - 5. Individuals who anticipate absence or travel throughout the study that would interfere with their ability to complete the analysis at the mid-point and end of challenge.
  - 6. Patients with a peanut, tree nut, or olive oil food allergy or intolerance.
  - 7. Patients who are unable or unwilling to travel to Auburn University main campus for live health and wellness challenge events, individual assessments, personal appointments, and pre- and post- data collection
  - 8. Individuals who have NOT been stabilized on medication to treat or manage high blood pressure, high cholesterol, dyslpidiemia, or pre-diabetes for at least 12 weeks prior to the study.
  - 9. Patients who do not have access to the internet and therefore unable to complete the education portion of the study
  - 10. Individuals who have a pacemaker
  - 11. Patients who decline participation during informed consent

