### 4.2. Research design and methods

- Participants will be seen at the Auburn University Pharmaceutical Care Clinic (AUPCC) for their initial "Healthy Tigers" Healthy Hearts Program consenting visit. The assessment will include a health and wellness interview, International Physical Activity Questionnaire, Diet History Questionnaire II, a Mediterranean diet knowledge/adherence survey, and the completion of the eligibility form. During this visit, the letter of consent will be given to and discussed with the participant. If the participant chooses to participate, their signature will be obtained on the consent form.
- 2) a) Participants will then return to the Auburn University Pharmaceutical Care Clinic (AUPCC) for their baseline "Healthy Tigers" Healthy Hearts Program visit. Pharmacists and pharmacy residents, employed by the AUPCC will obtain the following: height measurement (inches), weight measurement (pounds), Calculated BMI (kg/m2) measurement of body composition (using bioelectrical impedance analysis) (% body fat, pounds of fat, pounds of lean mass, pounds of total body water), waist measurement (inches), hip measurement (inches), Waist to Hip Ratio, Waist to Height Ratio, Systolic blood pressure (mmHg), Diastolic blood pressure (mmHg), resting pulse (bpm), fasting blood glucose (mg/dL), fasting total cholesterol (mg/dL), fasting LDL-cholesterol (mg/dL), fasting HDL-cholesterol (mg/dL), fasting Triglycerides (mg/dL), total Cholesterol to HDL ratio, Atherosclerotic cardiovascular disease risk (ASCVD) Score (%), fasting insulin mI/L, fasting leptin ng/mL, IL-6 (pg/mL), tumor necrosis factor-α (pg/mL), urinary tyrosol and hydroxytyrosol. These measurements will be repeated at week 6 and week 12 of the trial.
  - b) At this baseline appointment, the patient will also receive a baseline medication therapy management (MTM) assessment by a pharmacist in order to identify any potential or actual drug-related problem (DRPs), and to monitor for efficacy and safety of all medications, make recommendations for vitamins, minerals, and supplements, and provide preventative care recommendations (such as immunizations, osteoporosis screenings, colonoscopy, mammograms, and other recommended medical screenings that are recommended for the patient's age, gender, and concomitant disease states and medications).

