# **Total Participant Involvement Time**

#### 340 minutes

- 5) STUDY REQUIREMENTS
  - a) The participants will be asked to follow a dietary pattern that is associated with their assigned intervention group. The Mediterranean Diet (MD) group will be given supplements of extra virgin olive oil (EVOO) and mixed nuts. Participants in this group will be asked use these supplements as a part of their daily intake. A total of 6 L of EVOO and 6 pounds of mixed nuts (3 pounds raw walnuts and 3 pounds raw almonds) will be administered throughout the study. Participants in the MD group will be given 3 L of EVOO and 3 pounds of mixed nuts at the baseline appointment asked to return unused portions of at their 6-week appointment. At that time they will be given a new supplementation of 3 L or EVOO and 3 pounds of mixed nuts. Participants will be given the same instructions for use and asked to return unused portions at the end of the study (week 12).
  - b) The participants might have follow-up appointments scheduled with the pharmacist within the AUPCC depending on the patient's personal care plan that is developed at baseline. For instance, if a patient has potential or actual drug-related problems that are identified on their baseline MTM appointment, then the pharmacist will schedule follow-up appointments that are appropriate for the problem and the plan of care that is developed to address these problems. This will be done consistently between all patients in the study, regardless of the randomization (the pharmacist and the will be blinded concerning which group the patient is randomized to concerning dietary intervention).
  - c) Narrated nutrition education presentations will be developed by a registered dietitians, dietetic interns, graduate students, and faculty. These presentations will be loaded on the "Healthy Hearts Program" website. The participants will be asked one presentation weekly for the first 6 weeks of the study and then one additional education module at week 9. A post-presentation assessments will load after the presentation is completed, and completion of the assessment will be used as verification that the participant watched the presentation.
  - d) The participant will complete the following at baseline, week-6 and week 12 of the study: Diet History Questionnaire II, International Physical Activity Questionnaire, and a Mediterranean diet knowledge and adherence questionnaire.

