#### 4.5. Data analysis

Descriptive statistics will be conducted and presented for the population. Baseline demographics will be compared between the 2 groups and compared using the appropriate test for each data point. Continuous variables will be compared using student t-tests, categorical variables will be compared using chi-square tests, etc. Age will be collected as a continuous variable (years). Ethnicity will be collected as a categorical variable (Caucasian, Asian, African-American, Hispanic, Other, Not Reported). Level of education will be collected as a categorical variable (high school, some college, college degree, graduate degree, professional degree, etc.), smoking status will be collected as a categorical variable (never smoked, past smoker, current smoker), baseline ASCVD risk score (collected as a continuous variable), obesity (dichotomous), HTN (dichotomous), hypercholesterolemia (dichotomous), Number of patients with 1 disease state (continuous), number of patients with 2 disease states (continuous), number of patients with 4 disease states (continuous), number of yellow values (continuous), number of red zone values (continuous).

Baseline data on change in baseline body weight (%), change in total body weight (kg), calculated BMI (kg/m2) measurement of body composition (using bioelectrical impedance analysis) (% body fat, pounds of fat, pounds of lean mass, pounds of total body water), waist measurement (inches), hip measurement (inches), Waist to Hip Ratio, Waist to Height Ratio, Systolic blood pressure (mmHg), Diastolic blood pressure (mmHg), resting pulse (bpm), fasting blood glucose (mg/dL), fasting total cholesterol (mg/dL), fasting LDL-cholesterol (mg/dL), fasting HDL-cholesterol (mg/dL), fasting Triglycerides (mg/dL), total Cholesterol to HDL ratio, and ASCVD Score (%)) fasting insulin mI/L, fasting leptin ng/mL, IL-6 (pg/mL), tumor necrosis factor-α (pg/mL), urinary tyrosol and hydroxytyrosol, will be compared to data at week-6 and the end of the 12 weeks

- Student's T test will be used to compare the continuous data collected in the study
- Chi Square test will be used to compare the categorical data collected in the study

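### Baseline lipid-lowering drug use is known from the medication review but is not recorded as study data, tabulated by arm, used in the lipid comparison, or described as a stratification factor

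*Combined protocol and SAP*

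**What the plan says.** - **Outcome.** Section 2.1 sets the primary objective of this pilot as the effect of the Mediterranean diet (MD) versus the American Heart Association (AHA) intervention "on serum blood lipid levels as markers for cardiovascular disease risk".
- **Entry.** Section 3.1 counts several things as qualifying risk factors. One is "Have a pre-existing diagnosis of hypertension, pre-diabetes, or hypercholesterolemia". Another is "screening values classified in the 'yellow' or 'red' zone for" blood pressure, glucose or total cholesterol. Age, smoking, family history and ethnicity also count. None of these requires or forbids lipid treatment.
- **Medication criterion.** Exclusion 8 removes "Individuals who have NOT been stabilized on medication to treat or manage high blood pressure, high cholesterol, dyslpidiemia, or pre-diabetes for at least 12 weeks" before the study.
- **Randomization.** Section 1.2: "Patients will be randomized into two groups: the AHA vs MD". The other mention, in section 4.2 item 5(b), concerns consistent pharmacist follow-up ("This will be done consistently between all patients in the study, regardless of the randomization") and blinding. No ratio, sequence method, blocking or stratification factor is given.
- **Medication information.** In section 4.2, at the baseline visit, "the patient will also receive a baseline medication therapy management (MTM) assessment by a pharmacist". It covers all medications, and the visit information goes into the electronic medical record.
- **Study data.** The clinical data form in section 4.4 has no medication field. The only item from the medication review that section 4.5 names for collection is the number of drug-related problems.
- **Analysis.** Section 4.5: "Baseline demographics will be compared between the 2 groups and compared using the appropriate test for each data point". The variables listed include hypercholesterolemia as a yes/no item, but no drug use. Continuous outcomes are compared by Student's t test, with no covariate.

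**The concern.** Whether someone takes a lipid-lowering drug is a plausible strong predictor of their lipid level. In a small trial without stratification, the two arms can differ by chance in the share of users. A plain t test does nothing about that, and it leaves the variation due to drug use in the error term. The listed baseline variables would not show the imbalance directly, because a hypercholesterolemia diagnosis codes treated and untreated people alike.

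At stake are the precision and readability of the primary comparison, in a study whose results are meant for a dissertation and for publication. The information needed is already gathered at the baseline visit. This point concerns drug use at entry; drug changes during the trial are a separate matter that baseline adjustment does not solve.

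**Working it through.** **Can users and non-users both enter?** Section 3.1 admits people by diagnosis, by screening value or by non-lipid factors. Exclusion 8 might seem to make treatment uniform. Read strictly, it removes anyone not on stable medication; read loosely, it only requires those on treatment to be stable. Either way it joins blood pressure, cholesterol and pre-diabetes drugs by *or*. Someone stable on a blood pressure drug alone can therefore enter beside someone on a lipid drug. The mix remains.

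**Inputs.** The documents state no sample size, standard deviation, target effect or allocation ratio, so there is no figure to reproduce. Everything below is assumed, for scale only:
- total N of 40, 60 or 80
- share of users p of 30% to 50%
- LDL gap g between users and non-users of 20 to 40 mg/dL
- overall LDL SD of 35 mg/dL

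**Step 1: chance of a 20-point imbalance.** Take coin-flip allocation with K = pN users. The number of users in the MD arm is X ~ Bin(K, ½) and of non-users Y ~ Bin(N−K, ½). The difference in shares is X/(X+Y) − (K−X)/(N−X−Y). Summing the exact probabilities where its absolute value is at least 0.20:

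| N | p = 0.3 | p = 0.4 | p = 0.5 |
|---|---|---|---|
| 40 | 18.7% | 22.6% | 26.8% |
| 60 | 10.0% | 12.9% | 15.5% |
| 80 | 5.6% | 7.5% | 9.3% |

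Two independent binomials with equal arms give 23–27%, 12–15% and 7–9%. Coin-flip allocation with a random number of users gives 18–22%, 10–13% and 5–8%. Together these span about 5% to 27%. Fixing both the arm sizes and the number of users (hypergeometric) gives more, about 9% to 34%; there the difference moves in coarse steps and 20 points falls exactly on one.

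**Step 2: shift in an unadjusted comparison of week-12 levels.** Shift = imbalance × g:
- 0.20 × 20 = 4 mg/dL
- 0.20 × 40 = 8 mg/dL

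The standard error of an arm difference is 2 × 35/√N, which is 11.1, 9.0 and 7.8 mg/dL at N = 40, 60 and 80. The shift is thus about 4/11.1 = 0.4 to 8/7.8 = 1.0 standard errors.

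**Step 3: variance explained by drug use alone.** R² = p(1−p)g²/35²:
- smallest: 0.3 × 0.7 × 20²/1225 = 84/1225 = 7%
- largest: 0.5 × 0.5 × 40²/1225 = 400/1225 = 33%

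**Step 4: what remains once the baseline lipid is used.** If the gap is the same at baseline and week 12, it cancels in a change score. For adjustment on baseline LDL, let ρ be the baseline-to-week-12 correlation among people with the same drug status (assumed 0.5 to 0.8). Write b = p(1−p)g² and w = 1225 − b. The overall correlation is r = (b + ρw)/1225. The shift left after adjustment is 0.20 × g × (1−r). The further variance reduction from adding drug use is 1 − w(1−ρ²)/[1225(1−r²)].
- p = 0.5, g = 40, ρ = 0.5: r = (400 + 412.5)/1225 = 0.663. Shift left = 8 × 0.337 = 2.7 mg/dL. Further reduction = 1 − 618.75/686 = 10%.
- p = 0.3, g = 20, ρ = 0.8: r = (84 + 912.8)/1225 = 0.814. Shift left = 4 × 0.186 = 0.7 mg/dL. Further reduction = 1 − 410.8/413.9 = 1%.

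Most of the protection comes from the baseline lipid value; drug use adds about 1% to 10%.

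**The case against.** The strongest reply is that the t test remains valid. Randomization balances drug use in expectation, and the standard error already includes the variation it causes. A shift of 0.4 to 1.0 standard errors lies within the stated uncertainty. This stands. A reader might infer from the missing stratification that the lipid comparison is biased; the documents do not support that.

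Second, the 4 to 8 mg/dL applies only to raw week-12 levels. Section 4.5 speaks of comparing baseline with weeks 6 and 12, and does not say whether the between-arm test uses change, week-12 values or something else. On a change-score reading, a stable gap largely cancels. This also stands, so the figure should not be read as the error in the planned analysis. Equally, that protection is not written into the plan.

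Third, a reader might infer that the shift is as large as a diet effect. The documents state no expected or target effect, so that comparison cannot be made.

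Fourth, a reader might infer that the imbalance would be invisible. That is too strong. Hypercholesterolemia, risk score and zone counts are compared at baseline, lipids are measured then, and medications can be retrieved from the medical record. What is missing is the direct item.

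Finally, the absence of stratification is part of a wider silence: no randomization method is described. A stratified scheme is not ruled out, only not stated. None of these replies explains why a predictor already known at baseline is left out of the form, the table and the model.

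**Conclusion.** The point holds as an inexpensive improvement to precision and reporting. The documents establish that users and non-users of lipid-lowering drugs can both enter, that drug use is known at baseline, and that it appears in neither the data form, the baseline comparison nor the lipid analysis; no stratification is described.

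Its size rests wholly on assumed inputs. A chance imbalance of 20 points or more is plausible at 40 participants and uncommon at 80. It matters most if raw week-12 levels are compared. With baseline-lipid adjustment over half of the shift goes, and the extra gain from the drug-use term is modest. The case for including it is that it costs almost nothing and lets readers see the balance. The wording of exclusion 8 and the entry routes in section 3.1 that need no treatment must also be reconciled, since together they determine how mixed the population is.

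**What to change.** 1. Add one field to the section 4.4 form: lipid-lowering drug use at baseline (yes/no), taken from the medication review.
2. Add it to the baseline variables in section 4.5, by arm.
3. Replace the between-arm lipid t test with a linear model (ANCOVA) of the week-12 lipid on arm, baseline value of that lipid and baseline drug use. The within-arm question in Aim 1 is not affected.
4. If randomization has not begun, use permuted blocks stratified by the same yes/no factor, with allocation made after the baseline review is recorded. If it has begun, items 1 to 3 can still be done.
5. Reconcile exclusion 8 with the entry criteria in section 3.1.

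The cost is one form field, one table row, two model covariates (two degrees of freedom) and two randomization lists in place of one. The medication review must come before allocation, but checking exclusion 8 already requires medication status by then. The gain beyond baseline-lipid adjustment is small, so item 3 should not be reduced to drug use alone.

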#### 2. Purpose

#### 2.1. Purpose of this project including research questions and/or aims

The primary objective of this pilot study is to assess the efficacy of a MD intervention (education + EVOO and mixed nut supplementation) versus that of an AHA nutrition intervention (education) on serum blood lipid levels as markers for cardiovascular disease risk. As secondary outcomes we will assess insulin resistance, serum metabolic factors, blood pressure, body mass index, and waist circumference.

Research Question: In the Southeastern United States, is the dietary pattern of the American Heart Association or a Mediterranean style diet more effective in the reduction of CVD risk factors.

Aim 1: To assess whether or not patients have improvements in their CVD risk factors by the end of the 12-week program.

Aim 2: To assess which dietary intervention is most effective in the reduction of CVD risk factors at the end of the 12-week program.

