- c) All subjective and objective medical information collected during this appointment will be recorded in the CompuGroup Medical (CGM) electronic medical record (EMR) that is used in the Auburn University Pharmaceutical Care Center (AUPCC) and the "Healthy Tigers" programs. This EMR is a secure medical record that meets all HIPAA requirements and has been reviewed by the Harrison School of Pharmacy (HSOP) HIPAA officer, the Auburn University HIPAA officer, and the AU HIPAA consultant, and meets all legal and security requirements. These data will be perpetually stored in this EMR as required of medical data. Access to this EMR is restricted to authorized personnel only.
- 3) Baseline, 6 week and 12 week Appointments
  - a) Participants will then return to the Auburn University Pharmaceutical Care Clinic (AUPCC) for their baseline "Healthy Tigers" Healthy Hearts Program visit. Pharmacists and pharmacy residents, employed by the AUPCC will obtain the following: height measurement (inches), weight measurement (pounds), Calculated BMI (kg/m2) measurement of body composition (using bioelectrical impedance analysis) (% body fat, pounds of fat, pounds of lean mass, pounds of total body water), waist measurement (inches), hip measurement (inches), Waist to Hip Ratio, Waist to Height Ratio, Systolic blood pressure (mmHg), Diastolic blood pressure (mmHg), resting pulse (bpm), fasting blood glucose (mg/dL), fasting total cholesterol (mg/dL), fasting LDL-cholesterol (mg/dL), fasting HDL-cholesterol (mg/dL), fasting Triglycerides (mg/dL), total Cholesterol to HDL ratio, Atherosclerotic cardiovascular disease risk (ASCVD) Score (%), fasting insulin mI/L, fasting leptin ng/mL, IL-6 (pg/mL), tumor necrosis factor-α (pg/mL), plasma α linolenic acid, urinary tyrosol and hydroxytyrosol. These measurements will be repeated at week 6 and week 12 of the trial.

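### The primary objective covers a class of lipids, with no primary lipid, no multiplicity rule and no written form for the between-diet test

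*Combined protocol and SAP*

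**What the plan says.** Section 2.1 describes a pilot whose primary objective is the efficacy of MD versus AHA "on serum blood lipid levels as markers for cardiovascular disease risk". It then ranks other measures below the lipids: "As secondary outcomes we will assess insulin resistance, serum metabolic factors, blood pressure, body mass index, and waist circumference". No named lipid is moved to the secondary list, and none is put ahead of the others. Aim 2, the aim that compares the diets, is "To assess which dietary intervention is most effective in the reduction of CVD risk factors at the end of the 12-week program".

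Section 4.5 is the only analysis text. Its list of follow-up variables includes "fasting total cholesterol (mg/dL), fasting LDL-cholesterol (mg/dL), fasting HDL-cholesterol (mg/dL), fasting Triglycerides (mg/dL"), followed by the derived ratio of total cholesterol to HDL (TC:HDL), alongside weight, blood pressure, insulin, cytokines and other measures. Baseline data on these variables "will be compared to data at week-6 and the end of the 12 weeks". The test is given in one line: "Student's T test will be used to compare the continuous data collected in the study". The only comparison that section 4.5 writes out as being between the arms is at entry: "Baseline demographics will be compared between the 2 groups".

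Section 4.2 says of the clinical and laboratory panel, lipids included, that "These measurements will be repeated at week 6 and week 12 of the trial". A baseline value is therefore available for every lipid. The documents give no significance level, order of testing, multiplicity rule or sample size.

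**The concern.** A primary objective stated for a class of variables does not say which result answers it. Four lipid levels have an equal claim to be the primary result, and each would be tested without adjustment. The form of the MD-versus-AHA test is also unstated: it could compare week-12 values, changes from baseline, or week-12 values adjusted for baseline.

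The lipid and the test form could therefore both be chosen after the results are known. The study is labelled a pilot, but its stated objective is efficacy, its research question asks which diet works better, and section 2.2 plans a publication, a conference abstract and a dissertation. A single nominally significant lipid out of four could be presented as the primary finding, at an error rate well above the usual 5%.

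**Working it through.** The plan states no alpha, power or sample size, so it has no figure of its own to reproduce.

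**From the documents:** two arms; four lipid levels (total cholesterol, LDL, HDL, triglycerides); Student's t-test for continuous data; measurements at baseline, week 6 and week 12. Week 12 is taken as the between-diet time point because Aim 2 points there. TC:HDL is derived and is not counted.

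**Assumed, not in the documents:** two-sided 0.05 per test, no true effect, and the correlations and sample sizes given below.

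**1. Four independent tests.** Chance of at least one false positive = 1 − 0.95^4 = 1 − 0.8145 = 18.5%.

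**2. Four equally correlated tests.** Simulated chance that the largest |Z| of four exceeds 1.96 (1,000,000 draws per row):

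| Common correlation | At least one of four |
|---|---|
| 0 | 18.6% |
| 0.3 | 17.4% |
| 0.5 | 15.6% |
| 0.7 | 13.1% |
| 0.9 | 9.4% |

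The first row agrees with step 1 within simulation error. Against 5%, the range is 9.4/5 = 1.9 to 18.6/5 = 3.7 times nominal.

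**3. A lipid-shaped model.** Assumptions: 30 per arm; LDL mean 120, SD 35; HDL mean 50, SD 13; log-normal triglycerides with median 130 and log-SD 0.45; correlations HDL–triglycerides −0.4, LDL–triglycerides 0.1, LDL–HDL 0; baseline to week-12 correlation 0.7; total cholesterol = LDL + HDL + triglycerides/5. Results from 100,000 null trials:

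| Rule at week 12 | Chance of a false positive |
|---|---|
| Any of four, week-12 t-test | 15.0% |
| Any of four, change score | 14.9% |
| Any of four, baseline-adjusted | 15.1% |
| Holm over four | 3.9–4.0% |
| One named lipid, others tested only if it is significant | 4.8–5.0% |
| One named lipid at 5%, plus Holm on the other three regardless | 7.9–8.1% |
| One lipid, week-12 value or change score, whichever is significant | 9.1–9.3% |

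Among null trials with any significant lipid, 70–71% had exactly one. Varying the sample size (20, 30, 50 per arm) and the correlations over 243 settings gave 13.6–16.7% for any of four. Every setting kept the same SDs and the same formula for total cholesterol, so that range understates the uncertainty. The 9–19% from step 2 is the fairer range.

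**4. Illustrative cost of Holm.** The first step tests at 0.05/4 = 0.0125. The sample-size ratio at 80% power is ((z at 0.99375 + z at 0.80) / (z at 0.975 + z at 0.80))² = 1.42. With an assumed 30 per arm, the difference detectable with 80% power in an unadjusted t-test rises from 0.74 to 0.89 SD. At 0.74 SD, power falls from 80% to about 61%.

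**5. What baseline adjustment gives back.** At visit correlation 0.7 the residual SD is multiplied by √(1 − 0.7²) = 0.714. The detectable difference is then 0.53 SD at 5% and 0.63 SD at Holm's first step. A change-score t-test at 5% gives 0.736 × √(2 × 0.3) = 0.57 SD.

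**The case against.** The strongest reply is that the harm depends on a success rule that the plan does not contain. This is a pilot with no stated alpha and no confirmatory claim. Reporting every lipid with its estimate would be a defensible analysis, and strict family-wise control is partly a matter of preference. That limits the point to a low-cost improvement. It does not remove it, because the objective is efficacy, no feasibility objective is set, and publication is planned.

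Four stronger readings are tempting, and the documents do not support them:

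- **That one significant lipid will be declared a success.** No section says so. The defect is that no section excludes it.
- **That section 4.5 prescribes four between-arm lipid t-tests, or that it plans no between-arm test at all.** Neither is written. The follow-up sentence describes a comparison with baseline, and the between-arm test is inferred from the objective and Aim 2. The error rates above belong to that inferred analysis.
- **That the time point is wide open.** Section 4.5 lists week 6 and week 12 without ranking them, but Aim 2 largely settles week 12 for comparing the diets. Week 6 is therefore left out of the count.
- **That 15%, or the fall in power to 61%, is this trial's own figure.** Both rest on assumed inputs. The formula for total cholesterol is itself an assumption, and with the chosen SDs it makes total cholesterol and LDL correlate at about 0.93.

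**Conclusion.** The point holds as a cheap improvement. The primary objective names a class of lipids, section 4.5 gives no alpha or multiplicity rule, and the form of the between-diet test is left open. Under an assumed two-sided 0.05 per test and no true effect, the chance that at least one of four lipids is falsely significant at week 12 is about 15% in a plausible lipid model and about 9% to 19% over common correlations of 0.9 to 0. That is roughly two to four times nominal. Leaving the test form open for even a single lipid gives about 9%. The exact size depends on inputs that the documents do not supply, but every scenario examined exceeds 5%. The gap in the text does not depend on any of those inputs.

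**What to change.** Before any between-arm results are seen, amend sections 2.1 and 4.5 in one of two ways:

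1. Name one lipid, chosen by the sponsor, as primary, compared between arms at week 12 at two-sided 5%. Test the other three under Holm only if the primary is significant.
2. Keep all four lipids as primary at week 12, under Holm at a family-wise 5%.

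In both cases:

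- Replace the unadjusted t-test for MD versus AHA with one pre-specified analysis of the week-12 value adjusted for its baseline value, which is already collected.
- Report week 6, TC:HDL and the secondary outcomes as supportive, with estimates and 95% confidence intervals.
- Leave the research question and Aim 2 as they stand, on CVD risk factors in general, and add that results beyond the primary lipid analysis are supportive.

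The cost is wording only, with no new data. Under the first option, the other lipids cannot carry a stand-alone primary claim and are not formally tested if the primary misses. Under the second, power per test falls by the illustrative amount shown in the working, and baseline adjustment offsets part of that loss.
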